A Third-Wave Intervention for Internalized Weight Bias Combined With a Weight Loss
Program Using Video Conferencing Software

NCT Number: Not yet assigned

Document Date: 08/11/2022

Study Protocol & Statistical Analysis

Participants

Participants will be recruited for the study using an email Listerv announcement to individuals throughout the university and associated community. Participants must indicate that they are interested in weight loss and are interested in participation for the entire program before being accepted. Other inclusion and exclusion criteria require that participants be 18 or older, at a BMI of 25 kg/m² or greater, and are not pregnant or planning to become pregnant. Based on average scores for Durso and Latner's (2008) Weight Bias Internalization Scale and in staying consistent with Pearl, Wadden, Bach, Gruber, et al.'s (2020) research, individuals will also be screened for higher-than-average levels of IWBI, with a cutoff of 4 or higher. Individuals who have already successfully lost more than 5% of their body weight within the past six months will be excluded. Individuals with current use of medication prescribed for weight loss (such as orlistat, sibutramine, or rimonabant) will also be excluded. In addition, participants must have access to internet, along with a web camera and sound, and be able to use video conferencing software and attend weekly online groups. They will also need access to a reliable scale to weigh themselves weekly.

According to an a priori analyses run using G*Power, a sample size of 40 will be required to detect a medium effect size for a 2 x 2 repeated measures analysis of variance (ANOVA; Faul et al., 2007). A medium effect size was selected for a couple of reasons. First, this is consistent with previous literature, as Pearl, Wadden, Bach, Gruber, et al. (2020) also structured their methodology on detecting a medium effect size. Second, this study aims to examine the efficacy of an intervention. However, an intervention that produces only a small effect may be

less clinically meaningful than an intervention that produces a medium or large effect size. Due to attrition concerns, the sample size for the proposed study will be 70, with 35 individuals per group.

Interventions

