Participants will complete an initial digital screener to determine eligibility. Once it is determined that eligibility criteria are met, participants will be randomly assigned into one of two groups. Both groups will initially receive a weight loss intervention using the DPP through twelve weekly, hour long virtual sessions as led by clinical health psychology doctoral students with previous weight loss intervention experience. In addition, group leaders will look for opportunities to incorporate weight bias reduction strategies throughout the DPP when possible. However, only one group will be administered a third-wave, ACT and self-compassion-based IWB intervention for 30 minutes after the 60 minute weight loss intervention. Both groups will receive information on how to monitor eating behavior through MyFitnessPal, exercise through MyFitnessPal or smart devices, and will be encouraged to weigh themselves weekly or more. The IWB program will begin after the first four sessions of the DPP so that participants can spend the first month adjusting to weight loss treatment.

Measures

All measures will be completed at baseline and post-intervention online. Demographic information will also be collected at baseline. In addition, participant weight and height will be collected in person, using a digital scale and stadiometer, at baseline and post-intervention. If participants drop out of the study, they will be asked to complete the post-intervention surveys and attend a weigh-in, if possible.

Demographics. All participants will complete demographic questions assessing age, sex, gender, race/ethnicity, sexual orientation, income, education, and self-reported height and weight. Participants will also be asked about their desire for weight loss.

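### As written, a volunteer whose EDDS indicates bulimia nervosa can be randomised into the weight-loss program: no listed criterion excludes it, and the EDDS plays no part in entry

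*Combined protocol and SAP*

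**What the plan says.** **Eligibility (Participants).** The criteria are set out in some detail. They begin: "Other inclusion and exclusion criteria require that participants be 18 or older, at a BMI of 25 kg/m² or greater, and are not pregnant" (planned pregnancy also rules a person out). On internalized weight bias, "individuals will also be screened for higher-than-average levels of IWBI, with a cutoff of 4 or higher". Loss of more than 5% of body weight in the past six months excludes. So does current weight-loss medication: "Individuals with current use of medication prescribed for weight loss" are not eligible. The remaining conditions are interest in weight loss and in the whole program, suitable equipment, ability to attend online, and access to a scale.

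**Entry (Procedure).** "Participants will complete an initial digital screener to determine eligibility", and then: "Once it is determined that eligibility criteria are met, participants will be randomly assigned into one of two groups". No other condition for randomisation is stated.

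**What everyone randomised receives (Interventions, Procedure).** Both arms get the 12-week behavioral weight-loss program. "Both groups will receive information on how to monitor eating behavior through MyFitnessPal", and participants "will be encouraged to weigh themselves weekly or more".

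**The EDDS (Measures, Eating Behavior).** This 22-item questionnaire is described as assessing anorexia nervosa, bulimia nervosa and binge-eating disorder against DSM-5 criteria. Some items ask how often relevant behavior occurs. Kappa is given by disorder: .95 for anorexia, .71 for bulimia and .75 for binge-eating disorder. On timing: "All measures will be completed at baseline and post-intervention online".

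**The concern.** The trial collects information at baseline that could identify a person with active bulimia nervosa, but gives that information no role in deciding who is randomised. Whichever arm is drawn, the person then enters a program built around weight loss, tracking of eating and regular weighing. The stated measurement times are baseline and post-intervention, so no planned EDDS would pick up a problem while the program runs. Entry is the natural point at which to act.

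What is at stake is the safety of a small number of individuals. That active bulimia nervosa is a reason not to start such a program is a clinical judgement made here; the documents say nothing about the risk.

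**Working it through.** The plan states no figure on this point, so the first part of the check is textual.

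**Step 1: does any listed criterion keep bulimia nervosa out?** Take a volunteer with BMI 27, a weight-bias score of 5 and an EDDS result indicating bulimia nervosa.

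- Age, pregnancy, motivation, equipment: unrelated to bulimia nervosa.
- BMI floor of 25: met at 27. The floor would keep out low-weight anorexia nervosa, but not bulimia nervosa.
- Weight-bias cutoff of 4: met at 5.
- Loss above 5% in six months, or current weight-loss medication: neither identifies bulimia nervosa.

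If the volunteer also meets the unrelated conditions, every listed criterion is satisfied and the Procedure section sends the volunteer to randomisation.

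**Step 2: does the EDDS act as a gate anywhere?** It is described only under Measures. The text does not say whether baseline measures come before or after randomisation, but in either order no result is tied to entry. The Statistical Analysis Plan mentions maladaptive eating only as an exploratory outcome.

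**Step 3: would a questionnaire gate fit this design?** Yes. A weight-bias score already decides entry.

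**Step 4: how many people?** The documents give no prevalence. Assume a share p of 1% to 3% among otherwise eligible volunteers.

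- Expected among 70 = 70 × p: 70 × 0.01 = 0.7; 70 × 0.03 = 2.1.
- Chance of at least one among 70 = 1 − (1 − p)^70: 0.505 at 1%; 0.881 at 3%.

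**Step 5: what would an exclusion cost in recruitment?** Take the costliest case, in which every true case is flagged.

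- Volunteers needed = 70/(1 − p), rounded up: 70/0.99 = 70.7, so 71; 70/0.97 = 72.2, so 73.
- False positives: let f be the share of volunteers without bulimia nervosa who are flagged, assumed 1% to 5%. Flag rate = p + (1 − p)f.
  - p = 0.01, f = 0.01: 0.01 + 0.99 × 0.01 = 0.0199; 70/0.9801 = 71.4, so 72.
  - p = 0.03, f = 0.05: 0.03 + 0.97 × 0.05 = 0.0785; 70/0.9215 = 75.96, so 76.

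The range of 72 to 76 supposes that no false positive is cleared on follow-up. Clearing them moves the count back towards 71 to 73.

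**The case against.** **The rule may exist elsewhere.** The text refers back to material that is not supplied, and the screener items, the EDDS appendix and the consent pages are also absent. A reader might infer that the trial has no procedure for people who score positive. The documents do not support that: a referral or review step may be in the missing material, and no claim is made about it. What stands is narrower. The eligibility rules are stated in the text, and an exclusion is not among them. If one is already applied, writing it in costs a sentence.

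**The harm premise and the prevalence come from outside the documents.** Both are true and both are stated as such. This limits the point to an improvement; it does not remove it, because the change is nearly free.

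**It is not a statistical fault.** Agreed. A reader might infer bias in the randomised comparison or a contradiction in the text. Neither follows: the same entry rules apply before allocation to both arms, and the passages are consistent with one another.

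**Why stop at bulimia nervosa?** A reader might infer that anyone reporting compensatory behavior, or anyone with binge-eating disorder, should also be excluded. The first group is not defined in the text, no argument about harm to it is made here, and its size could drive the screening cost well above the figures shown. Binge-eating disorder is simply outside this point. The Mental Health section cites a binge-eating sample only as the source of a correlation with rumination. It is rumination that the section ties to aim three, so the passage settles nothing about who should be eligible.

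**A gate has side effects.** This stands. Bulimia nervosa has the lowest EDDS kappa of the three disorders, so misclassification in both directions should be expected. Volunteers also gain a reason to under-report.

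**Conclusion.** The point holds for the available text: the eligibility criteria do not exclude current bulimia nervosa, and the EDDS does not gate randomisation. Here EDDS-indicated means the questionnaire result, not a clinical diagnosis.

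The expected number affected is 0.7 to 2.1 of 70, resting wholly on the assumed 1% to 3%. The safety premise is general clinical judgement. The reading of the plan is limited by the missing screener items and appendices. It ranks as a cheap improvement for participant safety, with medium confidence, and changes no estimate, test or planned sample size.

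**What to change.** 1. For volunteers who meet all other criteria, complete and score the EDDS before allocation, and use that same administration as the baseline value.
2. Add one exclusion criterion: EDDS-indicated bulimia nervosa, by a scoring rule named in the protocol. Give anyone excluded referral information.
3. Allow a flagged volunteer to be enrolled only if existing study staff record, before allocation, that follow-up of the EDDS answers shows the criteria for bulimia nervosa are not met.

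**Cost.** No new instrument and no new staff. One to three extra otherwise eligible volunteers are needed at the assumed 1% to 3% (71 to 73 to reach 70). With the assumed 1% to 5% of false positives and none cleared, the number is two to six (72 to 76). Each flagged volunteer needs referral information or a short follow-up and record.

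**Downsides to accept and state.**
- Some false positives and some missed cases, given the kappa of .71.
- Some incentive to under-report on the baseline EDDS. This arises before allocation, so it should not differ by arm in expectation, but it can distort pre-post change on that scale.
- Slight truncation of the exploratory maladaptive-eating outcome at baseline.
- Slightly narrower generalisability.

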situation (i.e., “I am satisfied with the quality of the therapy I received” will be adapted to “I am satisfied with the quality of the telehealth weight loss treatment I received”). Similarly, questions about the therapist will be changed to “weight loss coach.” The STTS-R has been shown to have reliability for both the scale as a whole ($\alpha = .90$) and the subscales Satisfaction with Therapy ($\alpha = .91$) and Client Evaluation of Therapist ($\alpha = .80$).

Statistical Analysis Plan

All analyses will be conducted in SPSS 28 (IBM Corp., 2021). Data will be cleaned and screened before proceeding with analysis. Descriptive statistics will first be examined for the overall sample. Then, demographics among each group will be examined. Preliminary analyses will be run to ensure that there were no significant group differences in terms of basic demographics. Continuous variables will be examined using t-tests or ANOVA (for example, BMI) while dichotomous and categorical variables will be examined using chi-square (i.e., race/ethnicity). While it is hoped that randomization will provide even group characteristics, any potential group differences will be included as a covariate in analyses. Also, upon study conclusion, group differences will also be examined in terms of attrition and number of sessions attended to check whether treatment impacted these factors.

Hypothesis One and Hypothesis Two. A series of 2×2 (time x group) repeated measures ANOVA will be utilized to examine whether the BWLP only and Third-Wave + BWLP groups were successful with lowering weight, IWB, and weight bias and increasing healthy eating and physical activity and whether there are differences between the BWLP only group with the Third-Wave + BWLP group for each outcome.

Exploratory Analyses. Additional 2 x 2 RM-ANOVA's for each outcome variable, including depressive and anxious symptoms, rumination, maladaptive eating, self-esteem, cognitive flexibility and self-judgement will be examined.

Finally, significant changes in weight bias and IWB will be examined as predictors of weight loss and psychological outcomes.

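### The plan does not say how numeric covariates are centred; if one enters the repeated-measures ANOVAs as recorded, the test of change over time can refer to a person with covariate value zero

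*Combined protocol and SAP*

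**What the plan says.** The Statistical Analysis Plan section fixes three things.

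- Software: "All analyses will be conducted in SPSS 28".
- Covariates: baseline characteristics are compared between groups ("Continuous variables will be examined using t-tests or ANOVA (for example, BMI"), and "any potential group differences will be included as a covariate in analyses".
- Model: Hypothesis One and Hypothesis Two use a two-by-two design (visit by arm), described as follows: "repeated measures ANOVA will be utilized to examine whether the BWLP only and Third-Wave + BWLP groups were successful with lowering weight". The other main outcomes, including internalized weight bias, are handled in the same way. The second question put to this model is "whether there are differences between the BWLP only group with the Third-Wave + BWLP group for each outcome".

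The Demographics paragraph under Measures lists the candidate covariates: "assessing age, sex, gender, race/ethnicity, sexual orientation, income, education, and self-reported height and weight". The Participants section restricts entry to people "at a BMI of 25 kg/m² or greater" and aged 18 or older.

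The plan does not mention centring, the coding of covariates or estimated marginal means. It does not say which test decides whether the programmes succeeded.

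**The concern.** The same ANOVA is asked two questions: did weight, internalized weight bias and the other outcomes improve, and did the arms differ? In a 2 x 2 model with no named contrasts, the time main effect is the natural answer to the first question.

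A covariate measured once at baseline has the same value at both visits, so without a time x covariate term it cancels out of the within-person change. It can therefore adjust the time or time x group result only through that term. Once the term is in the model, the time main effect is the change where the covariate equals zero. With BMI or age in original units, zero lies outside the eligible population, and the test rests on a long extrapolation.

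Two errors can follow. A real average fall can be missed because the extrapolated estimate is very imprecise. If the covariate is related to change, a time effect can also be declared when average change is nil. The F statistic has no sign, so neither error is obvious from the ANOVA table.

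**Working it through.** **The plan's own figure.** The Participants section gives N = 40 for a medium effect. Alpha, power and the pre-post correlation are not stated, so 40 has no unique derivation. Assuming f = 0.25 and alpha 0.05, the within-person tests need exactly 40 at correlation 0.4 and power 0.80; at correlation 0.5, N = 40 gives power 0.869. The point does not depend on this figure. I use 40 (stated requirement) and 70 (planned enrolment) only as sample sizes.

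**Model.** With two visits, let D = post minus baseline and fit D = b0 + b1·group (−1/+1) + b2·X. The time test is the test of b0, and the time x group test is the test of b1. Replacing X by X minus its mean changes b0 and leaves b1 and its standard error unchanged.

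**Assumptions (not in the documents).** BMI mean 35, SD 6; age mean 45, SD 13; two-sided alpha 0.05; effects in SDs of D; equal groups.

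**Step 1: standard error.** The ratio of raw to centred SE of b0 is √(1 + (mean/SD)²·N/(N−1)).

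- BMI, N = 40: √(1 + 34.03 × 40/39) = 5.99. N = 70: 5.96.
- Age, N = 40: 3.65. N = 70: 3.63.
- Other BMI assumptions, from 32 (SD 5) to 38 (SD 8): about 6.5 to 4.9.

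**Step 2: power for a true fall of 0.5 SD, X unrelated to D.** The centred noncentrality is 0.5·√N; the raw value is that divided by the ratio; df = N − 3.

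| Covariate | N | Noncentrality, centred / raw | Power, centred / raw |
|---|---|---|---|
| BMI | 40 | 3.16 / 0.53 | 86.8% / 8.1% |
| BMI | 70 | 4.18 / 0.70 | 98.5% / 10.6% |
| Age | 40 | 3.16 / 0.87 | 86.8% / 13.5% |
| Age | 70 | 4.18 / 1.15 | 98.5% / 20.6% |

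For a fall of 1.0 SD with raw BMI at N = 70, power is 28%, against 100% centred.

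**Step 3: no mean change, but X correlated with D.** The slope is r/SD, so b0 = −r·mean/SD. For r = 0.3: −0.3 × 35/6 = −1.75. Its SE at N = 70 is √(1 − 0.09) × 5.96/√70 = 0.68, so the noncentrality is −2.58 and the rejection rate is 72%.

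| r (BMI) | N = 40 | N = 70 |
|---|---|---|
| 0 | 5% | 5% |
| 0.2 | 23% | 38% |
| 0.3 | 47% | 72% |

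Simulation with 10,000 runs per cell and BMI drawn afresh gave 22%, 36%, 46% and 71% for the four lower cells, and 5 to 6% after centring. A positive r (higher BMI, smaller fall) gives a false fall; a negative r gives a false rise. With a true fall of 0.5 SD, r = −0.3 and N = 70, the raw test showed a significant rise in 43% of runs. The time x group t statistic was the same raw and centred in every run.

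**Step 4: how often a numeric covariate enters.** Under randomisation with independent checks at 5% (level assumed), the chance is 1 − 0.95^k: 5% for BMI alone, 9.75% for BMI and age, 14.3% for three numeric variables. If a looser 10% level were used, two or three checks would give 1 − 0.9² = 19% and 1 − 0.9³ = 27%.

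**Step 5: weighting by the trigger.** With BMI the only numeric covariate and N = 70, overall power for the 0.5 SD fall is 0.95 × 98.5% + 0.05 × 10.6% = 94.1%. The overall false-positive rate at r = 0.3 is 0.95 × 5% + 0.05 × 71.8% = 8.3%.

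**The case against.** The case against has real force.

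- **Silence is not a rule.** A reader might infer that the plan prescribes uncentred covariates. It does not; it leaves the matter open, and an analyst could centre without departing from it. The gap still matters because nothing directs the analyst to do so.
- **The deciding test is not named.** The success question is put for both groups, so within-group change at the covariate mean would be a reasonable reading and would avoid the problem. The plan does not ask for it.
- **The harm is conditional.** A reader might apply the 72% or the 8% to the trial as a whole. Those figures hold only once a numeric covariate has entered; step 5 shows how far they shrink. About one trial in three (1 − 0.95^8 = 34%) would flag at least one of eight variables, but most of the listed demographics are categorical, so that figure should not be set beside the BMI results.
- **A false change needs a correlation.** At r = 0 the error rate stays at 5%. The loss of power needs no correlation.
- **The randomised comparison is intact.** A reader might infer that the test of the third-wave add-on is compromised. It is not. Both arms receive the weight loss programme, so the time effect is an uncontrolled before-after result.
- **Categorical variables.** A reader might infer that race/ethnicity would be entered as numeric codes. Nothing in the documents says so. An evenly split 0/1 covariate would inflate the SE only √(1 + (0.5/0.5)²) = 1.41 times, and zero would then be a real subgroup.

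These points limit the size and severity. They do not remove the gap.

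**Conclusion.** The point holds in conditional form. The plan fixes the software, the model and the covariate rule but leaves open where change over time is evaluated. If a numeric covariate enters as recorded and the time main effect is taken as the test of success, the answer can be badly wrong: power of about one in ten where it should be near 90% or more, or a spurious rise or fall where the covariate predicts change. The exact sizes rest on the assumed BMI and age distributions, effect sizes and correlations. The mechanism needs only that zero lies far from the data, which the eligibility criteria ensure. Because the trigger is uncommon and the between-arm test is untouched, I rate this minor to moderate, and worth correcting because correction costs nothing.

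**What to change.** Add to the Statistical Analysis Plan section, next to the covariate rule:

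- Numeric covariates are centred at the grand mean of the analysed sample before entry.
- Categorical covariates enter as factors.
- Success is judged from change over time, overall and within each group, estimated at the covariate mean with confidence intervals; this is the named test for the success part of Hypotheses One and Two, and for the exploratory outcomes analysed in the same way.

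The cost is two or three sentences. It needs no extra data, participants or visits, does not change the sample size, and leaves the time x group results as they would have been.

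### With two time points, the planned RM-ANOVA drops every randomised participant who has no post-intervention value, and the plan states no analysis population or missing-data method although it enrols 70 to secure 40

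*Combined protocol and SAP*

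**What the plan says.** - **Analysis.** Statistical Analysis Plan, in the paragraph on the two main hypotheses: "A series of 2×2 (time x group) repeated measures ANOVA will be utilized to examine whether the BWLP only and Third-Wave + BWLP groups" succeeded on weight, internalised weight bias, weight bias, diet and activity, and whether the groups differ on each. The software is SPSS 28. The exploratory outcomes use the same model.
- **Timing.** Measures: "All measures will be completed at baseline and post-intervention online". Weight is measured in person at the same two points.
- **Size.** Participants: "a sample size of 40 will be required to detect a medium effect size for a 2 x 2 repeated measures analysis of variance", then "Due to attrition concerns, the sample size for the proposed study will be 70, with 35 individuals per group". No expected dropout rate is given.
- **Retrieval.** Measures: people who leave are asked, where feasible, to complete the final surveys and be weighed.
- **Attrition check.** Statistical Analysis Plan, first paragraph: "group differences will also be examined in terms of attrition and number of sessions attended to check whether treatment impacted these factors".
- **Unequal burden.** Procedure: "only one group will be administered a third-wave, ACT and self-compassion-based IWB intervention for 30 minutes after the 60 minute weight loss intervention". This add-on starts after the fourth session. Under Interventions, it also involves keeping a journal.
- **Not stated.** There is no analysis population, imputation, mixed model or missing-data sensitivity analysis. The only remark on data handling is that data will be cleaned and screened.

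**The concern.** A standard repeated measures ANOVA needs a value at every occasion. With two occasions, a participant without the second contributes nothing, not even the baseline. The plan does not say this, but it follows from the method named. Both hypotheses are therefore tested on those who supplied post data rather than on those randomised.

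Two questions are exposed differently. Whether each group lost weight is distorted whenever leaving is related to outcome, even if it works identically in both arms. Whether the groups differ is distorted only if leaving works differently by arm. That is plausible here, because from the fifth session one arm attends for 90 minutes and the other for 60. The attrition comparison looks at how many leave, while bias also depends on who leaves.

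**Working it through.** **1. The plan's own figures.** Alpha, power and the pre-post correlation (rho) are not stated, so the 40 cannot be confirmed. Assume f = 0.25, two-sided alpha 0.05 and the time x group interaction, with noncentrality f² x N x 2/(1 - rho) on 1 and N - 2 df.
- rho = 0.4, N = 40: 0.0625 x 40 x 2/0.6 = 8.33, power 0.80. This reproduces 40 exactly.
- rho = 0.5, N = 40: 0.0625 x 40 x 2/0.5 = 10, power 0.87. At 80% power, 34 would suffice.

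So 40 is reachable. The implied allowance is (70 - 40)/70 = 42.9%, leaving about 20 observed per arm.

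**2. Size of the bias for weight.** All inputs are assumptions:
- week-4 loss has mean 1.5 kg and SD 1.5 kg;
- final loss has mean 4 kg and SD 4 kg, correlated 0.6 with week-4 loss;
- there is no true arm effect, and 35 per arm;
- the log-odds of dropout rise by a slope for each SD less lost by week 4.

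For two occasions the interaction test is the two-sample t-test on change. Expected final loss among those observed is 4 + 4 x 0.6 x (mean standardised week-4 loss among those observed). With slope 1 and 43% dropout that mean is about 0.36, so the observed mean is 4 + 2.4 x 0.36 = 4.86 kg against a true 4.0 kg. This is the within-group overstatement in any arm with slope 1.

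Bias in the arm contrast (simulated; two-sided 5% test):

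| Slopes by arm | Dropout | Dropouts returning data | Bias | Rejection rate |
|---|---|---|---|---|
| 1 and 1 | 43% | none | 0 | 5% |
| 1 and 0.75 | 43% | none | about 0.17 kg | 5% |
| 1 and 0.5 | 43% | none | about 0.4 kg | 6% |
| 1 and 0 | 43% | none | about 0.87 kg | 10% |
| 1 and 0 | 43% | 30% | about 0.5 kg | 7% |
| 1 and 0 | 43% | 50% | about 0.3 kg | 6% |
| 1 and 0 | 20% | none | about 0.4 kg | 7% |

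Arithmetic check of the 50% row: dropouts' mean standardised week-4 loss is -0.36 x 0.571/0.429 = -0.48. Among those observed it is (0.571 x 0.36 - 0.214 x 0.48)/0.786 = 0.13, and 2.4 x 0.13 = 0.31 kg.

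**3. The attrition check.** Power of the chi-square comparison at 35 per arm:
- 34% vs 51% (12/35 vs 18/35): 29%
- 30% vs 50%: 40%
- 20% vs 50%: 77%

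In the 1-and-0 rows above the dropout rates are equal, so this test has nothing to find.

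**4. What a model can repair.** In standardised units, with rho 0.5, 43% dropout and slope 1 in one arm only:
- Dropout depends on baseline: RM-ANOVA bias is about 0.17 SD, and a likelihood model that keeps all baselines has about 0.
- Dropout depends on the unseen post value: RM-ANOVA bias is about -0.18 SD and the likelihood model's about -0.28 SD.

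**The case against.** The protocol does more than count losses. Because it seeks post data from people who leave, those who return stay in the RM-ANOVA. A reader might infer a completers-only comparison, but the documents do not support that. It is an observed-case comparison, and successful retrieval can cut the bias by more than half, as the 50% row shows. What remains is that retrieval is best-effort, and the SAP does not say that retrieved data are analysed in the assigned arm.

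A reader might also infer that the attrition check cannot detect a problem, or that a null result would be taken as reassurance. It can detect a large imbalance, and it covers attendance too. No text says how a null result would be read. What stands is that it is weak for moderate gaps, blind to equal rates with different reasons, and does not alter the estimate.

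The 0.87 kg is a one-sided extreme, and nothing in the documents shows that poor responders leave more often. Milder differences between arms give 0.2 to 0.4 kg with rejection near 5 to 6%. This objection is right: bias in the arm contrast is a risk, not a finding.

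Finally, imputation is not a cure. Imputing from week-4 weight brings the simulated bias to about 0 only because dropout was made to depend on that weight alone. Home weights are encouraged but are not planned study data, and these weight simulations show nothing for the questionnaire outcomes.

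**Conclusion.** The concern holds as an omission with a predictable consequence. The stated method yields an observed-case result, and the plan names neither the population nor how missing values are handled, despite a sizing margin of 30 in 70. That part is certain from the documents and the method. The 43% is a margin, not a forecast.

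The size of any bias rests on the assumptions shown. If dropout depends on early loss at the assumed strength, within-group loss is overstated by about 0.86 kg on 4.0 kg, roughly a fifth, before any retrieval. The arm contrast ranges from 0 (same mechanism in both arms) to about 0.87 kg (slopes 1 and 0, no retrieval). The documents do not support saying that the between-arm result will be biased, or in which direction. The change should be made before analysis; the trial's design does not depend on it.

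**What to change.** - State that all 70 randomised participants are analysed in their assigned arm whatever their attendance, including post data retrieved from dropouts.
- Make the primary time x group contrast a multiple-imputation or likelihood (mixed-model) analysis that keeps every baseline. Use baseline outcome and sessions attended as predictors of the missing values, plus self-reported home weight where available. Attendance arises after randomisation, so it belongs in the imputation step and should not be an adjustment covariate in the arm comparison.
- Keep the observed-case RM-ANOVA as a sensitivity analysis.
- Keep the attrition comparison, and add a comparison of baseline characteristics between those lost and those kept, by arm.
- Add a missing-not-at-random sensitivity analysis, such as a delta shift for each outcome or return to baseline for weight, because step 4 shows that the primary model can fail when dropout depends on unobserved values.

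The cost is SAP wording and more analysis work, plus recording home weights if they are to be used. Within-group estimates will probably be smaller and intervals wider. Imputing by arm with about 20 observed per arm will be somewhat unstable, so the imputation model should be kept small.
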